## **1 STUDY OBJECTIVES**

### **1.1 Primary Objective**

SPECIFIC AIM 1: To determine the feasibility and acceptability of a telephone-delivered mindfulness training intervention (TMT) in decreasing caregiver burden among rural, informal caregiving teams caring for African Americans with dementia.

Hypothesis 1: TMT will be feasible within the informal caregiving teams. Feasibility is established when 85% (95% CI: 72.5, 97.5) of participants in the telephone-delivered mindfulness training intervention complete at least six sessions of the intervention.

Hypothesis 2: The adapted TMT will be acceptable to informal caregiving teams as evidenced by an 85% (95% CI: 72.5, 97.5) endorsement of the program in post-participation interviews.

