## **9 STATISTICAL CONSIDERATIONS**

### **9.1 General Design Issues**

Hypotheses related to the study are provided in this protocol. A single-arm, pre-post design will assess the primary outcomes of feasibility and acceptability. Eight weekly intervention sessions with a retreat is considered the minimum amount of time needed to deliver all components of the intervention. Please see Table 3 for reliability and validity information for each of the scales.

**SPECIFIC AIM 1:** To determine the feasibility and acceptability of a telephone-delivered mindfulness training intervention (TMT) in decreasing caregiver burden among rural, African American, informal caregiving teams of people with dementia.

**Hypothesis 1:** TMT will be feasible within the rural, African American, informal caregiving teams. Feasibility is established when 85% (95% CI: 72.5, 97.5) of participants in the telephone-delivered mindfulness training intervention complete at least six sessions of the intervention.

Hypothesis 2: The adapted TMT will be acceptable to rural, African American, informal caregiving teams as evidenced by an 85% (95% CI: 72.5, 97.5) endorsement of the program in post-participation interviews.

SPECIFIC AIM 2: To explore, on a preliminary basis, the effects of the training on caregiver burden and relevant secondary outcomes for both caregiving team members, including:

SPECIFIC AIM 2: To explore, on a preliminary basis, the effects of the training on caregiver burden and relevant secondary outcomes for both caregiving team members, including:

Hypothesis 1: Compared with baseline levels, we hypothesize that mindfulness training will reduce caregiver burden (Zarit Burden Interview).

Hypothesis 2: Compared with baseline levels, we hypothesize that mindfulness training will improve emotion regulation by increasing positive coping styles (acceptance, positive refocusing, positive reappraisal) and decreasing negative coping styles (rumination, catastrophizing, self-blame) as measured by the Cognitive Emotion Regulation Questionnaire.

Hypothesis 3: Compared with baseline levels, we hypothesize that mindfulness training will increase tolerance of uncertainty as measured by (an adapted form of) the Intolerance of Uncertainty Scale.

Hypothesis 4: Compared with baseline levels, we hypothesize that training in mindful communication will increase perceived social support among the caregivers (PROMIS Social Support short forms).

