## 9.2 Sample Size and Randomization

We calculated the effect size for the feasibility outcome, the acceptability outcome, and the Zarit Burden Interview. The sample size depends on the number of individuals who can reasonably participate in a telephone mindfulness intervention and takes into consideration the challenges of recruiting study participants in rural areas among underprivileged groups. We expect that no more than 8 caregivers could participate in a call at one time. Limiting the group size to 8 will ensure that all participants have an opportunity to contribute and that the instructor can keep track of all participants.

We anticipate being able to recruit no more than 36 CG-CP dyads in two years and expect a withdrawal rate of 10-15%. We anticipate having 32 dyads join the intervention and complete all baseline assessments and that 28 of those will complete all post-participation assessments. We will make every effort to follow-up with every participant, either in person or on the telephone, resulting in little missing qualitative data. We will use multiple imputation procedures to account for missing quantitative data.

Based on a sample size of 32 and a pre-post correlation of 0.5-0.7, we will have 75-80% power to detect a pre-post difference in the ZBI means of 3.3 – 4.2 consistent with an effect size of about 0.5 utilizing and alpha of 0.05. This effect size is consistent with those reported in other mindfulness interventions. The sample size of 32 with a feasibility of 85% would result in a 95% CI of 72.5 to 97.5. Similarly, a sample size of 32 with an acceptability of 85% (based on interviews with participants) will result in a 95% CI of 72.5 to 97.5. If we have higher than anticipated withdrawal rates, we will have lower precision.

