## 9.4 Outcomes

### 9.4.2 Primary outcome

- 1) The primary outcome is feasibility. We define feasibility as 85% of participants who start the intervention will complete at least 6 of the intervention sessions. Feasibility is measured by class session attendance records collected at the time of the calls by the instructor. The instructor will notify the project manager who attended the call and the project manager will document attendance in the REDCap database.
- 2) (Qualitative) A second primary outcome is acceptability. We define acceptability as 85% of participants expressing comfort with the majority of the intervention components and homework.

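### The 95% interval of 72.5 to 97.5 for both primary outcomes is a Wald interval whose limits sit about 3.5 to 4 points above Wilson's at 85% of 32, and the plan names no interval method

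*Combined protocol and SAP*

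**What the plan says.** Section 9.2 gives one precision figure for each primary outcome. For feasibility: "The sample size of 32 with a feasibility of 85% would result in a 95% CI of 72.5 to 97.5". For acceptability: "a sample size of 32 with an acceptability of 85% (based on interviews with participants) will result in a 95% CI of 72.5 to 97.5".

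The same limits are written into the Aim 1 hypotheses. Section 1.1 has "Feasibility is established when 85% (95% CI: 72.5, 97.5) of participants" and Section 9.1 has "an 85% (95% CI: 72.5, 97.5) endorsement of the program in post-participation interviews".

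Section 9.4.2 sets the success criteria on the observed proportion alone: "We define feasibility as 85% of participants who start the intervention will complete at least 6 of the intervention sessions", and "We define acceptability as 85% of participants expressing comfort with the majority of the intervention components and homework". Neither criterion mentions a confidence limit.

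No section names the method behind the interval. The quantitative plan in Section 9.5 covers outcomes 3 to 11. Feasibility and acceptability are outcomes 1 and 2, so the plan does not say how their intervals will be calculated in the report.

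**The concern.** The limits are symmetric about 85%, which points to the Wald formula. With 32 people and a proportion this close to 100%, the binomial distribution is clearly skewed. A symmetric interval then reaches too far up and not far enough down.

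This is the only numerical statement of uncertainty for the two primary outcomes. If its lower limit is too high, a reader planning a larger trial will set aside low completion or endorsement rates that 32 people cannot rule out. Because Section 9.5 names no method, the formula implied at planning could also carry over into the final report, where it behaves worst at the counts the study hopes to see.

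**Working it through.** **Inputs.** From Section 9.2: n = 32, p = 0.85, 95% level. Two-sided is inferred from the symmetric limits. Clustering of caregiver and care partner is set aside. Note that 0.85 × 32 = 27.2, which is not a whole count; the neighbours are 27/32 = 84.4% and 28/32 = 87.5%.

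**1. Reproduce the plan's figure.** Wald: p ± 1.96 √(p(1−p)/n). The standard error is √(0.85 × 0.15/32) = 0.0631 and the half-width 1.96 × 0.0631 = 0.1237, giving 72.6 to 97.4. The stated half-width is 12.5 points against 12.37, so each limit agrees within 0.13 point. A multiplier of 2 gives 72.4 to 97.6. A t multiplier (31 df) gives 72.1 to 97.9, and a continuity correction gives 71.1 to 98.9. Wilson and exact limits do not match.

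**2. Other intervals at the same inputs.**
- Wilson: centre (p + z²/2n)/(1 + z²/n) = (0.85 + 0.0600)/1.1200 = 0.8125. Half-width 1.96 √(p(1−p)/n + z²/4n²)/(1 + z²/n) = 1.96 × 0.0702/1.1200 = 0.1228. Result: **69.0 to 93.5**, width 24.6 points.
- Exact (Clopper-Pearson, beta quantiles at 27.2 of 32): **68.0 to 95.1**, width 27.1 points.

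The stated lower limit is 72.5 − 69.0 = 3.5 points above Wilson and 72.5 − 68.0 = 4.5 above exact. The stated upper limit is 97.5 − 93.5 = 4.0 above Wilson and 97.5 − 95.1 = 2.4 above exact. The stated width is 25.0 points, so the fault is location and not width.

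**3. Coverage at n = 32.** For each true rate, add the binomial(32, p) probabilities of the counts whose interval contains that rate.
- At a true rate of exactly 85%, the Wald interval contains the truth for counts 23 to 29: coverage 86.3%. It lies wholly above the truth at 30, 31 or 32 (8.5 + 3.1 + 0.6 = 12.2%) and wholly below at 22 or fewer (1.6%). Wilson covers 95.3% and exact 97.9%.
- That 86.3% is a local dip. Wald covers 94.5% at a true 85.5% and 94.0% at 86%, but 84.0% at 90% and 80.2% at 95%.
- On a grid of 1,501 true rates from 80% to 95%, Wald never reaches 95%. It averages 89.8%, lying wholly above the truth 9.4% of the time and wholly below 0.8%. Wilson averages 95.7%.

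**4. Behaviour at the counts around and above the 85% criterion** (28 to 32 meet it; limits in %).

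| Count | Wald | Wilson | Exact |
|---|---|---|---|
| 27/32 | 71.8 to 97.0 | 68.2 to 93.1 | 67.2 to 94.7 |
| 28/32 | 76.0 to 99.0 | 71.9 to 95.0 | 71.0 to 96.5 |
| 29/32 | 80.5 to 100.7 | 75.8 to 96.8 | 75.0 to 98.0 |
| 30/32 | 85.4 to 102.1 | 79.9 to 98.3 | 79.2 to 99.2 |
| 31/32 | 90.8 to 102.9 | 84.3 to 99.4 | 83.8 to 99.9 |
| 32/32 | 100 to 100 | 89.3 to 100 | 89.1 to 100 |

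Four of the five successful counts give a Wald interval that runs past 100% or has no width. At 30/32 the Wald lower limit lies above the 85% target, so rates below target would appear to be excluded; the Wilson and exact limits do not exclude them.

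**The case against.** The strongest reply is that nothing has been miscalculated. A standard formula applied to the plan's own inputs gives the stated limits, and the three sections agree with one another. That stands. A reader might infer an arithmetic error, or that the stated precision is wrong; the documents support neither, because the figure reproduces and its width is within half a point of Wilson's.

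A reader might also take 86% as the general coverage of the method. That is too strong. It belongs to one pair of n and p, and coverage at a true 85% is 94.6% with 31 people and 93.2% with 28. What holds more widely is the shortfall averaged over plausible rates and its one-sided direction.

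Third, the limits above 100% and the misses at 30 to 32 belong to intervals that the plan never prints, and Section 9.5 does not commit the team to Wald. Also true. Those results show why a method should be named; they do not show that the team will use the wrong one.

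Finally, no decision depends on the lower limit. Section 9.4.2 uses the observed 85%, and Section 9.2 bases the sample size on call capacity and recruitment. So the temptation to say that the feasibility or acceptability conclusion would change has no support. At 28/32, the smallest successful count, Wilson's lower limit of 71.9 is only 0.6 point below the printed 72.5. However, the printed interval is labelled for 85%, and Wald at 28/32 would start at 76.0.

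**Conclusion.** The point holds as a minor to moderate one. The interval printed for both primary outcomes is a Wald interval, too high at both ends for 85% of 32: by 3.5 points (lower) and 4.0 points (upper) against Wilson, and by 4.5 and 2.4 points against the exact method. Coverage at n = 32 averages about 90% over true rates of 80 to 95%, with nearly all the error on the optimistic side. What is affected is the uncertainty stated now and reported later. The 85% success rule, the sample size and the width are not materially affected.

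This rests on three assumptions: the plan's own denominator of 32, independent participants, and Wald as the source of the limits, which is inferred from the match because no method is named. Section 9.2 also says "We anticipate having 32 dyads join the intervention and complete all baseline assessments and that 28 of those will complete all post-participation assessments", so the acceptability denominator could be nearer 28. At 85% of 28, Wald gives 71.8 to 98.2 and Wilson 67.7 to 93.9, a displacement of about the same size.

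**What to change.** - **Section 9.5:** state that the feasibility and acceptability proportions will each be reported with a Wilson 95% interval. Exact intervals are an acceptable, slightly wider alternative, but one method should be chosen in advance.
- **Sections 1.1, 9.1 and 9.2:** replace the limits with 69.0 to 93.5 and label them as Wilson at 85% and n = 32. Alternatively, quote attainable counts: 68.2 to 93.1 at 27/32 and 71.9 to 95.0 at 28/32.
- Use the same method for whichever denominator is finally analysed, with any allowance for pairing that the team adopts.

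The cost is wording in four sections and no new data. The quoted limits become about 3.5 to 4 points less favourable.

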### 9.2.1 Treatment Assignment Procedures

This is a single-arm study. Randomization and masking do not apply.

## 9.3 Interim analyses and Stopping Rules

We do not plan an interim analysis. The study will be stopped if 3 or more individuals have a serious adverse event probably or definitely related to the study.

## 9.4 Outcomes

### 9.4.2 Primary outcome

- 1) The primary outcome is feasibility. We define feasibility as 85% of participants who start the intervention will complete at least 6 of the intervention sessions. Feasibility is measured by class session attendance records collected at the time of the calls by the instructor. The instructor will notify the project manager who attended the call and the project manager will document attendance in the REDCap database.
- 2) (Qualitative) A second primary outcome is acceptability. We define acceptability as 85% of participants expressing comfort with the majority of the intervention components and homework.

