## 9.5 Data Analyses

This is a single-arm pilot feasibility study with one baseline and one post-intervention measure.

Quantitative variables

For all quantitative questionnaire measures (outcomes 3-11), the change in the measure from baseline to post-participation is the outcome. First, we will examine variable distributions and missing data patterns. Next, we will conduct exploratory, descriptive analyses to assess *patterns of change* associated with participation in the programs for each of the variables including proximal mediating outcomes, intermediate outcomes (secondary stressors), and distal health outcomes. Because all analyses are exploratory, we will next perform bivariate assessments utilizing a paired t-test, analyzing caregivers and care partners separately. We do

not plan to adjust for multiple comparisons, but will interpret results conservatively and with great caution.

We will also explore the use of multivariable methods to enable us to control for variables that could influence the outcomes. Adjusted models will utilize repeated measures mixed models with individuals nested in families as random effects. We will control for the baseline FAST score (severity of dementia) and the relationship to the care recipient (spouse, adult child, other relative). In this small study (32 dyads), it will not be possible to formerly assess subgroups defined by gender. However, we will produce descriptive statistics by gender and age group.

We plan to invoke an intention-to-treat analysis in dealing with missing data using multiple imputation or full information maximum likelihood methods.

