### Qualitative variables

We will collect three types of formal qualitative data: 1) telephone interviews with key informants; 2) interviews with CG and CP prior to and following each 8-week class; and 3) transcriptions of audio-recorded classes. See key informant topics above. We will use the insights from key informants to adjust the intervention including the content and the logistics as needed.

Pre-participation interviews will address participant expectations and concerns about the research process in general and the intervention in particular.

Post-participation interviews will address CG/CP's attitudes and experiences with the intervention, including:

- The most memorable aspects of the class sessions;
- The perceived value and cultural congruence of the mindfulness training;
- The usefulness, challenges, and recommended changes in intervention components or language;
- The perceived value of various intervention components for management of stress related to caregiving or family conflict;
- Their recommendations for tools that might help maintain practices, if desired;
- Their unfulfilled expectations of the intervention;
- The usefulness of the technology components (e.g., call-in lines and/or tablets).

Each interview will be audio-recorded and transcribed. Using transcripts of key informant interviews and post-participation interviews, two or more research team members will apply a thematic analysis strategy, coding each transcript and identifying themes within and across interviews, with subsequent discussion of themes among members of the qualitative analysis team and resolution of discrepancies. The qualitative analysis team, who will include the PIs and [name], among others on the study team, will categorize the themes and present them to the Advisory Council for further input. Results will inform improvements in subsequent iterations of the intervention as well as the development of larger-scaled interventions.

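### Acceptability, the second primary outcome, is worded in two ways, and the documents give no rule for turning an interview into the yes/no value that its 85% mark and confidence interval need

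*Combined protocol and SAP*

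**What the plan says.** Section 9.4.2 labels acceptability as qualitative, makes it the second primary outcome and gives its definition: "We define acceptability as 85% of participants expressing comfort with the majority of the intervention components and homework". The hypothesis in section 1.1, repeated in 9.1, looks for "85% (95% CI: 72.5, 97.5) endorsement of the program in post-participation interviews". Section 9.2 treats acceptability as a proportion, taking "a sample size of 32 with an acceptability of 85% (based on interviews with participants") and giving a 95% interval of 72.5 to 97.5. Section 9.1 also plans to compare acceptability rates between groups with and without tablets. Section 3 applies the outcome to caregivers and to care partners.

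The data come from the post-participation interview. Sections 6.1.4 and 9.5 list its topics: memorable aspects, value and cultural fit, usefulness, challenges and suggested changes, help with stress, tools for keeping up practice, unmet expectations, and technology. For the analysis, 9.5 says that "two or more research team members will apply a thematic analysis strategy, coding each transcript and identifying themes within and across interviews". The team then talks the themes through and settles any disagreements. The qualitative team includes the investigators.

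**The concern.** Endorsing a program is one overall judgement. Comfort with most of its parts is a count. A person can satisfy one and not the other, and the text does not say that the second wording is how the first will be measured.

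The larger gap is between the interview and the percentage. A proportion with a binomial interval needs each person recorded as accepting or not accepting. Thematic coding describes what people said, within and across interviews. The planned resolution of discrepancies concerns themes, not the classification of a person. If no rule exists elsewhere, the result of a primary outcome would depend on decisions about wording, components, homework and mixed answers that the plan leaves open, made by a team that includes the investigators.

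**Working it through.** **1. The plan's own interval.** Inputs from 9.2: p = 0.85, n = 32. The standard error is √(0.85 × 0.15 / 32) = 0.0631, and 1.96 × 0.0631 = 0.1237. The interval is 85% ± 12.4 points, or 72.6 to 97.4, against 72.5 to 97.5 stated. Working back from the stated half-width, n = 0.85 × 0.15 × (1.96 / 0.125)² = 31.3. The stated figure is therefore a rounded Wald interval for one binary value on each of 32 people. The arithmetic is not in dispute; the binary value that enters it is undefined.

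**2. The two primary outcomes side by side (9.4.2).**
- *Feasibility:* the denominator is those who start the intervention, the cut-off is six sessions, the source is the attendance record, and the instructor and project manager record it.
- *Acceptability:* a percentage and a phrase. No list of components, no interview item, no statement of what counts as comfort, no named person who makes the call, and no handling of mixed or missing interviews.

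**3. What *majority* would mean.** The documents do not tie *components* to one list.
- With the three emphases in the précis, a majority is 2 of 3.
- With the eight sessions plus retreat in Table 1, it is 5 of 9.
- If homework is one more item in the count, these become 3 of 4 and 6 of 10.
- If homework must be accepted in its own right, a person comfortable with all three emphases but not with homework fails. If homework is one item, the same person has 3 of 4 and passes.

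**4. Whether the described interview supplies the value.** Neither post-participation topic list names comfort or homework. The list in 9.5 does reach component level, but through usefulness, challenges and perceived value. Table 2 schedules homework assessments, and the calls in 6.1.3 ask about practice; neither is said to record comfort or to feed this outcome.

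**5. Where the mark falls.**
- Per role, n = 32: 0.85 × 32 = 27.2, so 28 are needed. 27/32 = 84.4% misses; 28/32 = 87.5% meets.
- Both roles pooled, n = 64: 0.85 × 64 = 54.4, so 55 are needed. 54/64 = 84.4% misses; 55/64 = 85.9% meets.

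In either case one person classified differently can change the verdict. No figure in the documents shows how many people would be classified differently under the two wordings or by two coders.

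**The case against.** The strongest reply is that sections 1.1 and 9.1 state a hypothesis and 9.4.2 defines its term, so there is one definition with a person-level threshold built in. That is a fair reading and may be what was meant. It does not supply a usable rule, because the components are not listed and no described question asks about comfort with each.

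A second reply is that the topic lists are not the interview guide, and that manuals exist outside these documents: a procedures manual for data collection (10.1), one covering interview technique and recording (10.3.1), and an instructor's manual detailing the components (5.2). Any of them could hold a rule. This stands as a limit on the point. A reader might infer that acceptability will necessarily be scored only after the interviews are heard; the documents are silent on that and do not establish it.

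Three other stronger readings do not hold:
- A reader might infer from "For all quantitative questionnaire measures (outcomes 3-11), the change in the measure from baseline to post-participation is the outcome" that acceptability was deliberately left without a quantitative analysis. That range also omits feasibility, which is plainly a proportion, and 9.2 gives acceptability a proportion and an interval. What is missing is the step from interview to value.
- A reader might infer that anyone who accepts most components but rejects homework is counted differently under the two homework readings. Someone with 2 of 3 components and no homework has 2 of 4, which is not a majority, and so fails under both. Counts of homework rejecters needed to change the verdict would require knowing how many components each accepted.
- A reader might take "28 of those will complete all post-participation assessments" to mean that only 28 people per role will be interviewed. The 28 refers to dyads completing every assessment. Section 9.2 expects little missing interview data, and 6.1.4 seeks a final interview regardless of attendance.

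Finally, one person deciding the result is true of any 85% mark at n = 32, feasibility included. That is correct. It matters more here because feasibility is read from attendance records and acceptability rests on judgement. The study is a single-arm pilot, and no section ties missing 85% to stopping or progression, so the stakes are limited.

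**Conclusion.** The point holds and should be fixed. As written, the plan does not describe how the yes/no value behind its second primary outcome is collected or derived, and it words the outcome in two ways without linking them. The size is a sensitivity: at n = 32 the mark lies between 27 and 28 people, and the rate of disagreement between wordings or coders is unknown. The conclusion assumes that no rule is held in a manual or interview guide outside these documents. If one is, the remedy reduces to stating it in the protocol and aligning the wordings. Nothing here questions the stated interval or the use of thematic analysis to explain the result.

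**What to change.** - Use the 9.4.2 definition in 1.1 and 9.1, and list the components it covers.
- State whether homework must be accepted in its own right or is one item in the majority. Only the first guarantees that a person who rejects homework is not counted as accepting.
- Add a closed yes/no comfort item for each listed component and for homework to the post-participation interview.
- If interviews are already done, have the existing coders independently apply a written yes/no rule, fixed before any proportion is calculated, and report their agreement before discussion.
- Report caregivers and care partners separately, each with the number interviewed out of the number who attended the first session, which is how 6.1.2 defines an intervention participant.
- Counting people not interviewed as not accepting may be shown as a sensitivity result but need not be the headline. It mixes lost contact with dislike; section 8.1 expects some withdrawals after the care recipient's death. If 4 of 32 were not interviewed, all 28 others would have to accept to reach 28/32.
- Keep the thematic analysis as explanation.

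The cost is a few closed questions in an interview already planned, or one more coding pass, plus wording changes. The downside is slightly more burden for participants or coders and possibly a lower acceptability figure.
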